10.0 Analysis Sets

For the Double-Blind Treatment Phase: The safety analyses will be conducted on the safety population. The mITT population will be used for efficacy analysis. The PK population will be used for PK analyses. Patients will be analyzed according to randomized treatment assignment for efficacy assessments and according to actual treatment received for safety assessments. Patients will be analyzed by treatment, active arms pooled, and overall (where appropriate).

For the OLE Phase: The Open-Label safety population will be used. After completion of the 3-week Titration Period, patients will continue to receive pitolisant at a target dose of 17.8 mg (ages 6 to <12 years), 26.7 mg (ages 12 to <18 years), 35.6 mg (ages 18 to 65 years), unless they were not titrated to the target dose and are receiving a lower dose based on clinical response and/or tolerability, so all patients will be analyzed under the total treatment group.

[figure not shown]
10.1 Modified Intent-to-Treat Population

The mITT population will include all randomized patients who received at least one dose of study drug and have one Baseline and at least one post-baseline assessment at any visit of any endpoint during the Double-Blind Treatment Phase. This population will be used to summarize the primary and other efficacy data. Patients will be analyzed according to randomized treatment assignment.

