7.3.1. Titration Period, Double-Blind Treatment Phase (Days 1 to 21)

Patients will take their first dose of blinded study drug on the day after the Baseline Visit and will be titrated to their randomized stable dose during a 3-week Titration Period. The first dose of study drug will be Day 1, and study drug dose will be titrated on Day 8 and again on Day 15 (as appropriate based on randomized stable dose, as described in Table 7); all patients will be at their randomized stable dose of study drug by Day 15.

No on-site study visits are scheduled during the Titration Period in the Double-Blind Treatment Phase. Patients and/or their caregivers will be contacted by the study site by telephone on Days 8 and 15 (±3 days; TCs 1 and 2, respectively) to assess for AEs and concomitant medication use, complete the C-SSRS, and review/confirm titration of study drug dose.

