9.3.1. Intent-to-Treat Population

The ITT population will include all randomized patients who received at least one dose of study drug and have one baseline and at least one post-baseline assessment at any visit of any endpoint. This population will be used to summarize the primary and other efficacy data. Patients will be analyzed according to randomized treatment assignment.

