12.4 Efficacy Analyses

12.4.1 Double-Blind Treatment Phase

All efficacy analyses will be performed on the mITT Population. Results of the Double-Blind Treatment Phase will be reported following database lock once all patients have completed or discontinued the Double-Blind Treatment Phase of the study.

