12.4.1.2 Missing Data Imputations

No explicit imputation will be performed for the primary analysis; however, the MMRM model will yield unbiased results under the assumption that data are missing at random.

A sensitivity analysis for the primary endpoint (change from Baseline in mean ESS-CHAD [parent/caregiver version] score) will be performed using a hypothetical strategy. In this approach,

the unobserved data following discontinuation for lack of efficacy or AEs will be assumed to follow the placebo distribution at the matching visit, conditioned on the patient's observed data (including Baseline). Missing data after a patient discontinues treatment (for reasons other than lack of efficacy and AE) and intermittent missing data will be assumed to be missing at random. Details for the imputation are provided in this section.

Patients who discontinue early from the Double-Blind Treatment Phase study drug will be asked to return to the clinic for an Early Termination (ET) visit for completion of assessments (schedule of assessments in Appendix 7). The ESS-CHAD (parent/caregiver version) score collected at ET visit will be mapped to be closest analysis visit based on the rules defined in section 9.2. A multiple imputation approach will be utilized for missing data at Visit 3 (Day 22), Visit 4 (Day 50) and Visit 5 (Day 77, Week 11).

Table 7 represents the imputation rules for the primary endpoint sensitivity analysis. Missing data will be imputed using a three-stage multiple imputation (MI) approach.

Table 7: Post-Baseline Values Scenario and Imputation Methods

Study Medication	Analysis Visit			Imputation	
Status	Visit 3	Visit 4	Visit 5	Imputation	
	Present	Missing	Present	Intermittent missing data will be imputed within	
Completed/ Discontinued	Missing	Present	Present	treatment group using MI under a missing at random assumption with observed values at all	
	Missing	Missing	Present	available time points (including Baseline).	
Discontinued	Present	Present	Missing	Missing data after the discontinuation will be	
due to lack of efficacy or due	Present	Missing	Missing	imputed within the Placebo group (regardless of their assigned treatment group) using MI approach with observed values at all available	
to AE	Missing	Missing	Missing	time points (including Baseline).	

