Discontinued	Present	Present	Missing	Missing data after the discontinuation will be imputed within treatment group using MI approach with observed values at all available time points (including Baseline).	
due to any reason but lack of efficacy or	Present	Missing	Missing		
AE	Missing	Missing	Missing		

Abbreviations: AE = Adverse Event; MI = Multiple Imputation.

Note: Multiple imputation method is performed using the analysis visits, i.e., if the nominal result is missing, and there is an unscheduled result or if the ET result falls within the visit window that assessment will be used at that visit.

Step 1. Monotone Missing Pattern: Intermittent missing data will be imputed within treatment group using MI under a missing at random assumption with observed values at all available time points (including Baseline).

- a. From the analysis dataset containing the ESS-CHAD (parent/caregiver version) results, select all the patients (regardless of the discontinuation reason and status). The dataset will contain indicators variables for subject ID: SUBJID, planned treatment: TRTP, Baseline results: BASELINE, Visit 3 results: VISIT3, Visit 4 results: VISIT4 and Visit 5 results: VISIT5) and there will be one record per patient. Before transposing the dataset to get the required structure, if there are multiple non-missing records for a patient, select the record to include as per the rules defined in section 9.2.
- b. Using this dataset with treatment as covariate, imputed datasets (called imputations) will be produced using the Markov Chain Monte Carlo (MCMC) method implemented with the SAS MI procedure. The imputed datasets will contain the observed value (where it was not originally missing) or imputed values as per the model (for missing observations). The values imputed by MCMC method for the missing values will be used for patients who completed the treatment phase but have monotone patterns of missing data.

Step 2. Missing data for patients who discontinued for other reasons (i.e., not due to lack of efficacy or AE): Missing data after the treatment discontinuation (i.e., in the 'tail' end) will be imputed within treatment group distribution (intermittent missing data will have been imputed at the previous step). Patients who completed the treatment but have missing values not imputed at the previous step (i.e., at the 'tail' end) will have their missing imputed together with patients who discontinued for other reasons.

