- a. Using the dataset created in step 1, select all the patients regardless of the discontinuation status and reason for discontinuation.
- b. Using this dataset, one imputation will be produced using the MCMC method implemented with the SAS MI procedure. The values imputed by MCMC method for the missing values will be used for patients who discontinued treatment for reason other than lack of efficacy or AE.

Step 3. Missing data for patients who discontinued due to lack of efficacy or AE: Missing data after the treatment discontinuation will be imputed using the placebo group distribution, regardless of their assigned treatment group. The control-based pattern imputation will be implemented by breaking the imputation process into a sequence of multiple calls to PROC MI, where each call is intended to impute missing values at one time-point only, so the sequence will be repeated for each visit (Visit 3, Visit 4 and Visit 5).

- a. From the dataset created in step 2 and for the patients who discontinued due to lack of efficacy or AE, set to missing the results that occurred after the last visit performed for those patients (the last visit performed corresponds to the last analysis visit with no missing data prior to imputation).
- b. Split the dataset into 2 datasets:
 - O Dataset 1 includes all the patients in the placebo group (regardless of the discontinuation reason and status) as well as all the patients in the other treatment

groups (low dose pitolisant and high dose pitolisant) who discontinued treatment before Visit 3 due to lack of efficacy or AE.

- o Dataset 2: includes all the other patients.
- c. Using this dataset, one imputation will be produced using a monotone regression controlled for Visit 3 implemented with the SAS MI procedure (variables order will be Baseline and Visit 3). Once the imputation has been performed all patients who discontinued treatment due to lack of efficacy or AE in the active group will have Visit 3 data imputed.
- d. The dataset generated by the MI procedure (step 3c) will be appended to the dataset 2 (step 2b). This dataset will include all the patients.
- e. The previous steps (b to d) are repeated for each visit (Visit 4 and Visit 5).

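### Restricting the placebo-based sensitivity analysis to mITT can leave out the earliest AE/lack-of-efficacy dropouts, for whom SAP Table 7 and Step 3b give an imputation rule

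*SAP*

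**What the plan says.** **Population.** SAP 12.4.1 states: "All efficacy analyses will be performed on the mITT Population". SAP 10.1 admits randomised and dosed patients only if they "have one Baseline and at least one post-baseline assessment at any visit of any endpoint during the Double-Blind Treatment Phase". Protocol 9.3.1 has the same rule under the name ITT ("have one baseline and at least one post-baseline assessment at any visit of any endpoint"), and SAP 6.1 says that only the name changed.

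**Imputation.** SAP Table 7 has three rows for patients who stop for lack of efficacy or an AE. In one of them Visits 3, 4 and 5 are all missing. Their data after stopping are to be "imputed within the Placebo group (regardless of their assigned treatment group) using MI". Step 3b puts with the placebo patients those in the other "groups (low dose pitolisant and high dose pitolisant) who discontinued treatment before Visit 3 due to lack of efficacy or AE", and Step 3c expects their Visit 3 value to be filled in. Step 1a says to "select all the patients (regardless of the discontinuation reason and status" from the ESS-CHAD analysis dataset. It does not say whether that reaches beyond mITT.

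**Data collection.** Protocol 7.3.1 says: "No on-site study visits are scheduled during the Titration Period in the Double-Blind Treatment Phase". Contact before Day 22 is by telephone on Days 8 and 15, with AEs and the C-SSRS recorded. A patient who stops study drug is required to attend an early termination (ET) visit with the Visit 5 assessments (Schedule of Assessments, footnote f). Protocol 4.4.1, 7.3.3 and 9.1.3 describe attendance in softer terms, as something to be attempted or requested.

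**The concern.** The imputation rule and the population rule do not fit together for one kind of patient: an active-arm patient who stops during titration because of an AE or lack of efficacy, does not attend the ET visit, and has only telephone contacts afterwards. Table 7 and Step 3b provide for this patient. The mITT criterion may remove the patient first.

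Such a patient has no post-baseline ESS-CHAD and so adds no outcome to the primary MMRM. The placebo-based analysis is the only planned analysis of the primary endpoint that could count the patient, and it would count the patient as placebo-like. Leaving the patient out makes the result depend on what happened after randomisation. If more of these patients are in an active arm, it also makes the check somewhat lenient.

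**Working it through.** **Step 1. Who reaches the rule.** mITT entry needs any endpoint, whereas Table 7 concerns ESS-CHAD only. The four cases for a patient who stops for an AE or lack of efficacy are:

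| Patient | Post-baseline ESS-CHAD | In mITT? | Handling |
|---|---|---|---|
| Stops before Visit 3, attends ET | Yes; normally mapped to Visit 3 (window Day 2 to 35, SAP Table 5) | Yes | Later visits imputed from placebo |
| Stops before Visit 3, no ESS-CHAD, but another endpoint recorded at a visit | No | Yes | All-missing row; Visits 3, 4 and 5 imputed from placebo |
| Stops before Visit 3, no ET, telephone contacts only | No | Depends on whether a call is a visit | If not: excluded and never imputed. If so: as the row above |
| Stops after Visit 3 or Visit 4 | Yes | Yes | Covered by the later passes of Step 3 |

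Only the third row is a gap. The documents do not settle the telephone question. Protocol 6.5.6 lists study visits and telephone calls as separate things. SAP 9.6 refers to the safety follow-up contacts, which are calls under Protocol 7.5, as visits. AEs, the C-SSRS and ADAMS are listed endpoints in SAP Table 3.

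**Step 2. The plan's own figures (Protocol 9.2).** Inputs: 20 patients per group, SD 5 to 6, a difference of 3.9 for pooled pitolisant (40) against placebo (20), 95% confidence, two-sided tests (SAP 12.4.1.1). The alpha of 0.05 is inferred from the 95% interval.
- Half-width = 1.96 × SD × √(1/20 + 1/40) = 2.68 at SD 5 and 3.22 at SD 6. The plan says 2.7 and 3.2.
- Power at SD 5 = 80.0% (noncentral t, 58 df) or 81.3% (normal). The plan says 80%.

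Both reproduce, and this point disputes neither.

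**Step 3. Size of the gap, for illustration.** Assumptions: k of the 20 high-dose patients are in the third row; the effect in the rest is 3.9, which is the pooled planning figure borrowed for the high-dose contrast; those imputed from placebo have zero mean benefit; SD 5; no placebo patient is excluded.
- Contrast with the k patients included = 3.9 × (20 − k)/20.
- Change per patient = 3.9/20 = 0.195, about 0.2 points.

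| k | Contrast, k left out | Contrast, k included | Power, k left out | Power, k included |
|---|---|---|---|---|
| 0 | 3.90 | 3.90 | 67.1% | 67.1% |
| 1 | 3.90 | 3.71 | 66.0% | 62.7% |
| 2 | 3.90 | 3.51 | 64.7% | 58.1% |
| 3 | 3.90 | 3.32 | 63.3% | 53.3% |
| 4 | 3.90 | 3.12 | 61.8% | 48.5% |

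Power is for a two-sample t-test of 20 − k against 20 (left out) and 20 against 20 (included). It ignores the baseline covariate, the repeated measures and the imputation variance, so it shows direction and scale only. For the pooled contrast the change is 3.9/40, about 0.1 points per patient.

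**Step 4. Could it change a reading?** At SD 5 and k = 2, the comparison of 18 with 20 reaches p < 0.05 from an observed difference of about 3.29. With the two patients included, the difference in the rest would have to be about 3.56. Only results between these two values would change sides. At SD 6 and a difference of 3.9, t is 2.00 without the two patients and 1.85 with them. Both are below the critical value, which is 2.03 for 18 against 20, so that example shows dilution and no change of conclusion.

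**The case against.** A reader might infer that the mITT rule removes everyone in Table 7's all-missing row, or that the sensitivity analysis misses the dropouts it was written for. The documents support neither. The row is about ESS-CHAD, and any other post-baseline endpoint at a visit keeps the patient in mITT. The ET visit is required and includes ESS-CHAD. Step 3 runs for all three visits, so later AE and lack-of-efficacy dropouts are fully covered.

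It is also fair to say that an affected patient must meet several conditions at once, and that none of them may exist. If the calls on Days 8 and 15, or the follow-up calls 15 and 30 days after the last dose, count as visits, the criterion excludes close to nobody. No document gives a rate for this pattern, so k = 1 to 4 is assumption.

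A reader might further infer that the omission must favour the high dose. Protocol Table 7 shows a higher starting dose in the high-dose arm for adolescents and adults. In children aged 6 to under 12, however, the two active arms take the same dose through Day 14, and lack-of-efficacy stopping could fall on placebo. The direction is plausible but not established.

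Finally, this is a secondary check in a proof-of-concept trial without formal multiplicity control, and no decision rule hangs on it.

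All of this limits the size of the point. It leaves the mismatch between SAP 10.1 and Step 3b in place, because the documents support both readings of a telephone contact and the two readings give different analysis sets.

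**Conclusion.** The point holds in a narrow form. Because SAP 12.4.1 ties the placebo-based analysis to mITT, dosed patients who stop for an AE or lack of efficacy before Visit 3, miss the ET visit and have only telephone contacts can be excluded, although Table 7 and Step 3b provide for them. All other AE and lack-of-efficacy dropouts are handled as intended.

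Each such high-dose patient left out is worth about 0.2 ESS-CHAD points in the high-dose contrast. That rests on an assumed 3.9-point effect in the rest, zero benefit in those imputed, and 20 patients per arm. The number of such patients is unknown and may be zero. The primary MMRM and the sample size are not affected. This is a cheap improvement to one sensitivity analysis and does not undermine the trial's main result.

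**What to change.** Add one sentence to SAP 12.4.1.2 and 12.4.1.3.4: this sensitivity analysis includes all randomised patients who took at least one dose and have a baseline ESS-CHAD, analysed by randomised arm. The all-missing row of Table 7 and Step 3b then apply to everyone who fits them, and for this analysis it no longer matters whether a call is a visit.

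Protocol 1.3.2 describes the double-blind phase as completed. If its analysis is already final, report the result as a labelled supplementary analysis.

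No new table is needed to see whether the point matters. SAP 12.1.1 already plans counts of randomised-and-treated patients and of each analysis set, and SAP 10.0 provides for presentation by treatment. The difference per arm is the number excluded from mITT. If it is zero in every arm, one line in the study report closes the matter.

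The cost is one sentence and one rerun of code already specified. The only downside is a sensitivity estimate that may be slightly less favourable.

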10.3 Open-Label Safety Population

The Open-Label safety population will include all patients who are enrolled in the OLE Phase (i.e., eligible) and take at least one dose of open-label study drug.

10.4 Pharmacokinetic Population

The PK population will include all patients who received at least one dose of study drug and have a non-missing pitolisant PK concentration. Patients will be analyzed by treatment (high dose and low dose), active arms pooled, and overall (placebo patients will be excluded from the PK population).

11.0 Interim Analyses

No interim analysis will be performed.

12.0 Statistical Methods

All analyses will use SAS version 9.4 or higher. The analysis shells for the tables, listings, and figures will be provided in a separate document.

Categorical variables will be summarized using counts and percentages based on the specified population total. Percentages will be rounded to one decimal place, except 100% will be displayed without any decimal places and percentages will not be displayed for zero counts.

Continuous data will be summarized using non-missing observations (n, mean, SD, median, minimum, and maximum). The median, minimum, and maximum values will be displayed to the same level of the precision as the raw value. Mean and median will be rounded to 1 decimal place greater than the precision of the original value. The SD will be rounded to 2 decimal places greater than the precision of the original value. Confidence intervals, least square (LS) means, and standard error (SE) will be provided as appropriate. Confidence intervals, LS means will present the same precision as the mean value whereas SEs will present the same precision as SD.

P-values will be rounded to 4 decimal places. P-values less than 0.0001 will be presented as "<0.0001" and p-values greater than 0.9999 will be presented as ">0.9999."

For safety laboratory parameter and ghrelin levels, results reported as "<xx" will be imputed to xx; and result reported as ">xx" will be imputed to xx.

Statistical hypothesis testing will be and carried out at the level of significance.

The study objective is to evaluate the effectiveness of pitolisant in treating EDS and other symptoms of PWS for the purposes of informing the design of future studies in patients with PWS, a rare pediatric neurodevelopmental disorder. As such, the relative strengths of all measures are of interest and p-values will be reported with no formal multiplicity adjustments.

All the listings will be displayed by treatment arm, patient identifier and date of assessment. Age, sex, and race will be presented.

12.1 Patient Disposition

12.1.1 Disposition

When the Double-Blind Treatment Phase is complete, the number and percentage of patients screened, randomized, randomized and treated, randomized and not treated, completed the Double-Blind Treatment Phase, discontinued from the Double-Blind Treatment Phase, and eligible to enter in the OLE Phase will be summarized, together with a breakdown of the corresponding reasons for discontinuation from study drug and from the study. The number and percentage of patients included in each analysis set will be summarized as well.

The number of patients who screen failed and the reason for screening failure will be tabulated. A supportive data listing will be provided for the screening failure patients and will include the reason for screen failure and the list of inclusion/exclusion criteria failed.

For the OLE Phase, the number and percentage of patients who were treated in the OLE Phase, who completed or discontinued from the OLE Phase, and who discontinued from study drug in the OLE Phase along with the associated reasons for discontinuation from the study drug and/or the OLE Phase will be summarized.

Patient disposition data will be presented in a data listing for Double-Blind safety and Open-Label safety.

12.1.2 Important Protocol Deviations

All protocol deviations identified during monitoring or from data cleaning are recorded in the clinical trial management systems. However, deviations pertaining to unblinding information (i.e., a patient has received the incorrect kit and did not receive the treatment they were randomized to) will be programmatically derived. Those deviations will be deemed important deviations relating to study drug.

Based on all treated patients, the number and percentage of patients with important protocol deviations by category will be summarized by treatment arm, active arms pooled, and overall for the Double-Blind Treatment Phase and overall for the OLE Phase.

Important protocol deviations will be listed, and all COVID-19-related protocol deviations will be listed separately.

